7.3 The Judge-Advisor System (JAS)

A key component of the dynamics in a JAS is the differentiation between the roles of the judge and the advisor(s). The judge is the decision maker who assesses the information concerning a specific decision and makes the final decision. An advisor is the person who offers advice, information, or suggestions to the judge (Snizek and Buckley, 1995). While actual decision-making power resides solely with the judge, the advisor may have some stake in the judge's decision (Snizek and Buckley, 1995).

Using advice is an essential practice in making decisions in real life, whether it is as simple as seeking directions in an unfamiliar environment or more complex situations such as those involving legal or medical issues (Yaniv, 2004b). Advice is usually sought from someone with more expertise or providing a different perspective, because of a need to improve the accuracy of a judgement and the expectation that advice will help (Snizek and Van Swol, 2001, Yaniv, 2004b). In the context of prognostication, a doctor may also seek advice for social reasons, including self-affirmation and sharing of responsibility, knowing the difficulties of prognostication and having concerns about the consequences of making an inaccurate prediction (Kennedy et al., 1997, Yaniv and Milyavsky, 2007). The JAS offers a robust basis from which hypotheses on advice-giving in dyads or groups can be tested (Van Swol and Snizek, 2005).

7.4 JAS Research

In traditional JAS research, judges are asked to complete an experimental task that usually requires a quantitative answer. Judges provide an initial estimate and they may also be asked to express a level of confidence regarding the accuracy of this initial decision (Bonaccio and Dalal, 2006). Next, the judge will receive advice, which could come from a real advisor or could be fictional, depending on the aims of the study. The judge is then invited to reconsider the initial estimate and provide a final, possibly revised estimate. Research has focussed on the importance (weighting) that a judge gives to the advice provided and the level to which the judge incorporates this into their decision or not (discounting). When revising estimates, people tend to use two strategies: choosing between two estimates or averaging them. A surprising result of previous research has been that averaging was the more effective strategy across a wide range of commonly encountered environments. Authors have observed that despite this finding, choosing was the preferred strategy although greater accuracy would have been achieved had they always averaged (Soll and Larrick, 2009).

One of the main findings reported in the literature is that people tend to discount advice (Yaniv, 2004b, Yaniv and Kleinberger, 2000b, Bonaccio and Dalal, 2006). Although the appropriate use of advice leads to better judgements (because of the reduction of random error), respondents prefer their own estimates; this is referred to as egocentric discounting (Yaniv and Kleinberger, 2000a). Additionally, the distance of the advice from one's own opinion can affects the weight it receives. High-knowledge respondents discounted the advice given while the low knowledge group averaged less and chose to remain with their own initial judgment more (Yaniv, 2004b).

7.5 JAS research in the context of this study

While research is available on advice and information seeking among clinicians (Rappolt, 2002, Weber et al., 2007, Weinberg et al., 1981) to the best of our knowledge no experimental studies have used the JAS to explore the dynamics of receiving and using advice in the context of medical prognostic decision-making.

In the context of our study, it is often the responsibility of a (senior) doctor to formulate a prognosis to consider hospice enrolment, assess eligibility for a clinical study, plan care and treatment, and prepare patients and families. As described above, doctors could obtain advice in a formal MDT setting or ask a more experienced colleague, a colleague from a different background that brings a different perspective, or a colleague who has spent more time with the patient. JAS studies have used different types of questions, including estimations of the dates of historical events and multiple-choice questions (Bonaccio and Dalal, 2006). The current study will ask participants to estimate the probability of patients surviving two weeks (0-100%).

A recent series of experiments using a variety of judgement tasks has shown that, contrary to prior work, people placed a higher weight on advice from an algorithm as compared to advice from another person (Logg et al., 2019). The researchers provided judges in the study with equivalent advice that was labelled as coming from an algorithmic versus human source. In the first experiment, judges were asked to estimate the weight of a person in a photograph. The actual weight of this person was 164 pounds. All judges then received the same advice (163 pounds), which was the estimate provided by 415 participants in another experiment (Moore and Klein, 2008). Half of the judges were told that: 'An algorithm ran calculations based on estimates of participants from a past study. The output that the algorithm computed as an estimate was: 163 pounds'. The remaining judges were told that 'The average estimate of participants from a past experiment was: 163 pounds'. In this study, we will do an experiment similar to this, by randomising clinicians to receive equivalent advice, described as coming from a prognostic tool or another professional.

This research will provide greater understanding of the factors affecting the quality of MDT prognostic estimates and will provide an evidence-base to improve clinician training.

8 Assessment and Management of Risk

The table below summarises the risks and mitigations of all study procedures:

Intervention	Potential risk	Risk Management
Completion of an online experimental task to provide five prognostic estimates and receive prognostic advice from an 'advisor'	There are no obvious risks associated with the completion of this task. However, predicting survival is a difficult task, therefore participants may experience some feelings of frustration.	Participants will be advised that they can withdraw from the study at any time and without giving a reason.
Collection of data, using a secure online platform.	There is a small risk that data could be lost or accessed by unauthorised personnel.	Data will be encrypted, backed up and stored securely on UCL computers.

9 Objectives

To understand how clinicians form intuitive judgements about the prognoses of palliative care patients after receiving advice perceived as coming from either a team member or an algorithm.

9.1 Primary objective:

To assess the level to which clinicians incorporate advice received from other clinicians or an algorithm into their estimates of the prognosis of palliative care patients.

9.2 Secondary objective:

To investigate the extent to which clinicians' integration of advice is influenced by the characteristics of the judge, the advisor or the advice itself.

10 Study design

Study data will be collected using two different recruitment methods (arm A and arm B). Both study arms involve participants being asked to provide a prognostic estimate of the probability of survival for palliative care patients. Participants are asked to provide information about their gender, age, role, grade and experience. They will be presented with five case summaries ("vignettes") (see Appendix 2 – Sample vignette) based on real cases derived from a previous study (PiPS2) (Kalpakidou et al., 2018). In the PiPS2 study, data were collected on palliative care patients in order to calculate a prognostic score (the PiPS score). Doctors and nurses were asked to make a prediction about how long they expected the patient to survive, and the subsequent length of survival of the patients was recorded. We will create vignettes using the anonymised data already collected as part of the PiPS2 study (see Appendix 2 – Sample vignette). Participants will be presented with key prognostic information and will be asked to estimate the probability that the patient will survive the next two weeks (0% 'certain to die' to 100% 'certain survival').

Participants will be randomised into one of the following two groups: The clinicians' advice group or the algorithm advice group. In the clinicians' advice group, participants will receive advice labelled as coming from another clinician. Doctors will receive advice labelled as coming from nurses and *vice versa*. Seminar attendees with other clinical backgrounds in this group will be further randomised into receiving advice labelled as either coming from a doctor or a nurse. In the algorithm group, participants will receive advice labelled as coming from the PiPS-B algorithm. In fact, participants in both groups will receive the same advice. After receiving the advice, participants will be given the opportunity to give a revised estimate, in the light of the advice received.

A schedule of study assessments and procedures is set-out in Appendix 1 - Schedule of assessments.

11 Data collection and study procedures

We expect that data collection for this study will take approximately ten months starting in August 2020 and end by April 2021. See the Gantt chart in the appendix.

Clinicians will be invited to participate in the study as part of a (online) seminar on palliative care by the CI or through an invitation email sent to their hospice medical director (see section 12.3). Seminar participants will receive information about the study before the seminar and will be invited to complete the online questionnaire in preparation for the seminar. The CI will make it clear that delegates at the seminar are under no obligation to complete the questionnaire.

Participants will be provided with a link to the study website and will complete all assessments online. The website will provide information regarding the study and a link to a PIS. Participants will be asked to tick check boxes to indicate that they are giving informed consent. After filling in the demographics section, eligible participants will be considered to be enrolled and a participant ID will be assigned. Next, participants will be randomly allocated to one of the two study groups. This will be performed through the web-based system, using a pre-generated blocked randomisation list.

Participants will be given tailored instructions, shown a practice vignette and will then be able to start the decision tasks and to provide estimates of the probability of patients surviving two weeks. Participants will be presented with five vignettes. Vignettes will be presented in random order to prevent order effects.

There will be no time limit for completion, so that each participant will be able to consider their responses. Participants will be given the opportunity to log out and return to the same place at a more convenient time. Participants will not be able to move on to the next page if required information is missing or is in an incorrect format (e.g. incorrect email format). The online environment will be piloted by the study team in close collaboration with the study statistician who will review the data being collected before, during, and at the start of the recruitment phase to ensure data integrity.

After completing the series of vignettes, participants will be shown a debrief page to remind the participant what the results will be used for and they will be able to download a certificate of participation. Participants will be asked if they wish to receive a summary of the results at the end of the study and whether they would be willing to be approached for subsequent studies.

Responses collected through the website up until the scheduled seminar will be added to a spreadsheet to provide the attendees with preliminary study findings during the presentation.

12 Selection of Participants

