The secondary outcome will be clinicians' estimates of the probability of a patient surviving for two weeks. We will perform regression analyses to explore any associations between participants' weighting policies and characteristics of the participants (gender, age, work environment, role, seniority, expertise, confidence).

We want to explore any associations between participants' weighting policies and the advice itself (e.g. the strength of the advice) as well. Participants will receive five pieces of advice from the PiPS data. They will receive advice given with high confidence from 85% and upwards (i.e. the patient has 90% probability of surviving the next 14 days), with lower confidence (i.e. 75% probability of survival) and one where the advice is equivocal (i.e. 50% probability of survival). Multilevel regression analyses will be used to take into account multiple vignettes are completed by each participant.

17 Record keeping and archiving

At the end of the study, all essential documentation will be archived securely by the CI for a minimum of 20 years from the declaration of end of study.

Essential documents are those which enable both the conduct of the study and the quality of the data produced to be evaluated and show whether the site complied with all applicable regulatory requirements.

The sponsor will notify the research team when study documentation can be archived. All archived documents must continue to be available for inspection by appropriate authorities upon request.

18 Study Management Group (SMG)

The SMG will be formed of the CI ([name]) and all of the personnel listed in section 1. The group will meet regularly and will review recruitment figures and substantial amendments to the protocol prior to submission to the REC.

19 Ethics

The sponsor will ensure that the study protocol, PIS, consent form and submitted supporting documents have been approved by the appropriate Research Ethics Committee, prior to any participant recruitment. The protocol, all other supporting documents including and agreed amendments, will be documented and submitted for ethical and regulatory approval as required. Amendments will not be implemented prior to receipt of the required approval(s).

An annual progress report (APR) will be submitted to the REC within 30 days of the anniversary date on which the favourable opinion was given, and annually until the study is declared ended. The CI or delegate will prepare the APR.

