3.2.2 Secondary outcome measures

The secondary outcome will be clinicians' estimates of the probability of a patient surviving for two weeks and the characteristics of the participants (profession, gender, age, work environment etc.).

4 Statistical analysis plan

Data analysis will be mainly descriptive and focused on addressing the overall objective "To understand how clinicians form intuitive judgements about the prognoses of palliative care patients after receiving advice perceived as coming from either a team member or an algorithm".

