4.4 Analysis of the secondary objective

We will perform regression analyses to explore any associations between participants' weighting policies and characteristics of the participants (profession, gender, age, work environment etc.).

We want to explore any associations between participants' weighting policies and the advice itself (e.g. the strength of the advice) as well. Participants will receive five pieces of advice from the PiPS data. They will receive advice given with high confidence (i.e. the patient has 90% probability of surviving the next 14 days), with lower confidence (i.e. 75% probability of survival) and one where the advice is equivocal (i.e. 50% probability of survival).

Multilevel regression analyses will be used to take into account multiple vignettes are completed by each participant.

5 General statistical considerations

All the statistical summaries and analysis will be performed using Stata version 15 (or above).

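### A doctor–nurse difference in weight of advice, estimated across both groups, mixes the participant's profession with the advisor label (exploratory coefficient only, low priority)

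*Protocol*

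**What the plan says.** **Labels.** Protocol section 10 sets the label in the clinician group by profession: "Doctors will receive advice labelled as coming from nurses", and the reverse for nurses. Only seminar participants who are neither doctors nor nurses have the label ('doctor' or 'nurse') assigned at random. In the algorithm group everyone sees the same PiPS-B label.

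**Allocation.** Protocol section 11 allocates participants "using a pre-generated blocked randomisation list". It gives no ratio and no stratification by profession.

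**Objective.** Protocol 9.2 asks how far the use of advice is "influenced by the characteristics of the judge, the advisor or the advice itself". The Protocol Summary spells out the advisor characteristic as clinician against algorithm.

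**Analysis.** SAP 4.4 says: "We will perform regression analyses to explore any associations" between weighting policies and "characteristics of the participants (profession, gender, age, work environment etc". Protocol 16.2.3 plans the same for "characteristics of the participants (gender, age, work environment, role, seniority, expertise, confidence". Both add multilevel modelling for the repeated vignettes. Neither states a group term, a profession-by-group interaction, a label covariate or a restriction to one group for this analysis. SAP section 4 also states: "Data analysis will be mainly descriptive".

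**The concern.** For doctors and nurses in the clinician group, knowing the profession of the participating clinician (a judge, in JAS terms) is the same as knowing the label. If nurses there move further towards the advice than doctors, the data cannot say whether nurses take more advice or whether a 'doctor' label carries more weight.

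A regression of WOA on profession across all participants carries part of this mixture into its profession coefficient. A group main effect does not remove it, because the label differs by profession within the clinician group. The multilevel structure does not remove it either, because it deals with repeated vignettes.

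At stake is interpretation. A doctor–nurse difference reported as a characteristic of the participant could be partly or wholly a response to the label. A real difference could also be cancelled by the label.

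**Working it through.** **Inputs.** SD of WOA 0.3 to 0.4 and N of 100 to 300 (Protocol 16.1). The label rule comes from Protocol section 10. Assumed, because the documents do not give them: 1:1 allocation, the size and sign of L, the professional mix, and that the SD is that of a participant's mean WOA.

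**The plan's own figures.** Full 95% CI width = 2 × 1.96 × SD × √(4/N). For N = 100 this gives 0.235 and 0.314 (Table 1: 0.24 and 0.31). For N = 200 it gives 0.166 and 0.222 (Table 1: 0.17 and 0.22). All 12 cells reproduce, with N as the total in two equal groups. No stated figure depends on the present point.

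**What the coefficient estimates.** Let J be the nurse-minus-doctor difference under a common label, taken as equal for algorithm and human labels. Let L be WOA under a 'doctor' label minus WOA under a 'nurse' label.

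- Algorithm group, nurse minus doctor: J.
- Clinician group, nurse minus doctor: J + L.
- Both groups, with a fraction p in the clinician group: J + pL, so J + 0.5L at 1:1.

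Illustrations with assumed values:

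- J = 0, L = 0.20 gives 0 + 0.5 × 0.20 = 0.10, a difference where the judges do not differ.
- J = 0.10, L = −0.20 gives 0.10 − 0.10 = 0, a real difference hidden.
- L = ±0.10 shifts the coefficient by ±0.05, and L = ±0.05 by ±0.025.
- At p = 1/3 or 2/3, L = 0.10 shifts it by 0.033 or 0.067.

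A simulation of participant means (4,000 runs, N = 200, SD 0.3, J = 0, L = 0.10, equal doctors and nurses) gave 0.051 pooled, with and without a group main effect, 0.001 in the algorithm group and 0.101 in the clinician group. With 70% nurses among doctors and nurses, plus 20% other professions, it gave 0.050, −0.001 and 0.100. The shift does not depend on the mix.

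**Precision.** With nN nurses and nD doctors, V = SD² × (1/nN + 1/nD). The standard errors are √V pooled, √(2V) in the algorithm group and √(4V) for the interaction. At N = 200, SD 0.3, 100 of each: V = 0.09 × 0.02 = 0.0018, giving 0.042, 0.060 and 0.085. The 95% half-widths at N = 200, SD 0.3 to 0.4, are:

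- pooled: 0.083 to 0.111
- algorithm group: 0.118 to 0.157
- interaction: 0.166 to 0.222

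**Accuracy for J.** RMSE is √(0.25L² + V) pooled and √(2V) in the algorithm group. They are equal at |L| = 2√V. At |L| = 0.10:

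| N | Mix | SD | V | Pooled | Algorithm group |
|---|---|---|---|---|---|
| 100 | even | 0.3 | 0.0036 | 0.078 | 0.085 |
| 100 | even | 0.4 | 0.0064 | 0.094 | 0.113 |
| 100 | uneven | 0.3 | 0.0054 | 0.089 | 0.104 |
| 100 | uneven | 0.4 | 0.0095 | 0.110 | 0.138 |
| 200 | even | 0.3 | 0.0018 | 0.066 | 0.060 |
| 200 | even | 0.4 | 0.0032 | 0.075 | 0.080 |
| 200 | uneven | 0.3 | 0.0027 | 0.072 | 0.073 |
| 200 | uneven | 0.4 | 0.0048 | 0.085 | 0.098 |

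Even means equal doctors and nurses and no others. Uneven means 20% others and 70% nurses among the rest (56 and 24 at N = 100; 112 and 48 at N = 200). The pooled estimate has the lower RMSE in 7 of 8 rows. At N = 300 the break-even |L| is 0.069 to 0.092 (even) or 0.085 to 0.113 (uneven), so at 0.10 the algorithm-group estimate is better except with the uneven mix at SD 0.4 (0.080 against 0.075 pooled). At |L| = 0.05 the pooled estimate is better throughout.

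**Randomised label contrast.** Half-width = t × SD × √(2/n) per label. If other professions are 10% of 200, half fall in the clinician group, so n = 5: 2.306 × 0.3 × 0.632 = 0.44, or 0.58 at SD 0.4. With n = 10 it is 0.28 to 0.38.

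**The case against.** The strongest reply has four parts.

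**Nothing says the groups are pooled.** This is true; both documents leave the model open. They do not restrict it either, and a regression on participants' characteristics most naturally takes in all participants. The point therefore stays conditional.

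**The doctor or nurse label is not a stated target.** This stands. The Protocol Summary names clinician against algorithm as the advisor characteristic. A reader might infer that the advisor part of the secondary objective, or the primary comparison, is confounded. The documents do not support that: the contrast is randomised, and the label rule is part of the clinician condition. What remains is that the label enters the coefficient for the participant's profession, which is a target.

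**Cross-profession advice is deliberate.** This also stands. Protocol 7.5 values advice from "a colleague from a different background that brings a different perspective", so the label rule is not a design fault. The association between profession and WOA under that rule is a legitimate description, provided it is labelled as such.

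**Splitting by group may estimate J worse.** This stands at the planned sizes for |L| of about 0.10 or less. The SD assumption also matters. If the Protocol 16.1 figure is for a single judgement, an assumed within-participant correlation of 0.3 multiplies the standard errors by √((1 + 4 × 0.3)/5) = 0.66, and the break-even values fall in proportion, which favours the split. The thresholds are therefore indicative only.

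**Conclusion.** The point holds in a limited form. If the profession regression is run across both groups at 1:1, and J is the same under algorithm and human labels, its coefficient is J + 0.5L, and the plan says nothing that would separate the two parts. L is unknown in size and sign. The shift at an assumed |L| of 0.10 is 0.05, which is less than the pooled 95% half-width at N = 200 (0.083 to 0.111).

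Only one exploratory secondary coefficient is affected, so the change is optional and of low priority.

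Two further inferences would go too far. The algorithm-group difference is not a general judge effect, because the professions may differ in how they respond to an algorithm as against a person. For the same reason the profession-by-group interaction is not a pure label effect. If J does differ between the two kinds of label, the expression J + 0.5L and the RMSE comparisons no longer apply, although the mixing of judge and label in the clinician group remains.

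**What to change.** In SAP 4.4:

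- Keep the pooled profession coefficient, and say which participants and which group term the model includes.
- Add a profession-by-group term, and also report the doctor–nurse difference within each group with 95% confidence intervals.
- State the label rule beside the results: the pooled and clinician-group differences combine judge and label, and the algorithm-group difference applies under a common algorithm label.
- Do not interpret the interaction as a label effect.
- Take any 'doctor'-label versus 'nurse'-label estimate only from the other-profession seminar participants randomised to a label, and report it descriptively with n and confidence interval.

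The cost is SAP wording and one exploratory term. Profession is recorded before allocation (Protocol section 11), so no new data are needed. The price is precision: the by-group intervals are wider by a factor of √2, and the interaction interval by a factor of 2. The label estimate may rest on very few people, because hospice invitations go to doctors and nurses (Protocol 12.3.2). The gain is that a reader can see what each difference means.
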